7.7.2 PSA

PSA kinetics (e.g., PSA response and time to PSA progression) will be assessed at the time of the primary analysis of MFS according to the Prostate Cancer Clinical Trials Working Group (PCWG2) criteria.⁸

Summary tables and waterfall plots describing change in PSA relative to baseline will be reported at 12 weeks (or earlier for those who discontinue study treatment prior to 12 weeks), and separately, the maximum change at any time on study will also be reported for each patient using summary tables and waterfall plots.

ARN-509-003 Statistical Analysis Plan v7.0 26 June 2017

Page 19 of 34

PSA response rate will be summarized by treatment group. The relative risk (treatment:control) will be reported along with the associated 2-tailed 95% CIs. The two treatment groups will be compared using the stratified Mantel-Haenszel test.

The time to PSA progression will be calculated as the time from randomization to the time when the criteria for PSA progression according to PCWG2 are met + 1 day. Kaplan-Meier methods will be used to estimate the median time to PSA progression and 95% confidence intervals for each treatment group

7.7.3 Health-Related Quality of Life and Prostate Cancer-Specific Symptoms

The FACT-P and EQ-5D data will be scored and handled as recommended in their respective User's manuals, including handling of missing data both within the subscales and overall.^{9,10} All FACT-P and EQ-5D data analyses will be performed in the ITT population. On-study scores and change from baseline scores will be summarized and displayed graphically as appropriate.

A 10-point change in the FACT-P total score is considered clinically meaningful.¹¹ Therefore, any patient experiencing a 10-point decrease in FACT-P total scores from baseline at any post baseline time point will be considered to have experienced clinically meaningful deterioration in functional status. The proportions of patients with a 10-point decrement in FACT-P total score will be summarized by treatment group, and the two treatment groups will be compared using a Mantel-Haenszel test, stratified by PSADT (> 6 months vs. \leq 6 months), the use of a bone-sparing agent (Yes vs. No), and the presence of loco-regional disease (N0 vs. N1) at a two-sided 0.05 significance level.

The EQ-5D data will be summarized descriptively by treatment group and study visit.

Details on the PRO analyses will be provided in a separate PRO SAP.

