#### **8.9 LONG-TERM FOLLOW-UP**

- Obtain survival status, recording of development of symptomatic progression, initiation of any new systemic anti-cancer therapies, progression on first subsequent therapy (PFS2), and MRU every 4 months via clinic visit, telephone contact, or an alternative contact method per institution policy/practice. The FACT-P and EQ-5D questionnaires will be collected up to 12 months post-progression.
- **In addition, if patients discontinue study treatment prior to documented disease progression (ie, distant metastasis, see Section 7.1.8),** obtain CT of the chest, abdomen, and pelvis, plus bone scan and submit for BICR to evaluate for disease progression (every 16 weeks, until documentation of disease progression)

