#### **8.10 SUBSEQUENT THERAPY WITH ABIRATERONE ACETATE**

Due to local restrictions in Japan, the Sponsor will not provide abiraterone acetate and the criteria outlined in this section do not apply.

The Sponsor will provide abiraterone acetate to all other patients who meet the following criteria:

- patient signs informed consent to receive treatment with abiraterone acetate
- documented disease progression (ie, meet criteria for the primary endpoint [distant metastasis], see Section 13.2.1). If the study is unblinded, the requirement for meeting disease progression by BICR in Section 13.2.2 will not be required.

- the patient resides in a country in which abiraterone acetate and prednisone (or prednisolone) are indicated for the treatment of metastatic CRPC before chemotherapy
- the investigator caring for the patient decides that abiraterone acetate is the appropriate first subsequent treatment after discontinuation of study drug; and
- no other subsequent treatment has been prescribed after the progression event and before abiraterone acetate is prescribed.

Abiraterone acetate should be used according to the product label-prescribing information in the country of residence.

Prednisone (or prednisolone) should be used according to the product label-prescribing information in the country of residence. Prednisone (or prednisolone) will not be provided by the Sponsor, but should be prescribed as part of the regimen.

In countries where abiraterone acetate in combination with prednisone (or prednisolone) is not approved for the treatment of asymptomatic or mildly symptomatic mCRPC before chemotherapy, patients should be treated according to the local standard of care. Provision of abiraterone acetate will continue until the patient or investigator decides not to continue further treatment for any reason, unacceptable toxicity or the study is terminated by the Sponsor.

Serious adverse events will be collected during subsequent therapy with abiraterone acetate.

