### 13.4.3 Health-Related Quality of Life and Prostate Cancer-Specific Symptoms Analysis

The FACT-P and EQ-5D data will be scored and handled as recommended in their respective User's manuals, including handling of missing data both within the subscales and overall. All the analysis for FACT-P and EQ-5D data will be performed in the PRO population.

A 10-point change in the FACT-P total score is considered clinically meaningful. Therefore, any patient experiencing a 10-point decrement in FACT-P total scores from baseline will be considered to have experienced clinically meaningful deterioration in functional status. The proportion of patients with at least a 10-point decrement in FACT-P total score will be summarized by treatment arm. The decrement in the FACT-P total score between treatment arms will be compared using a Mantel-Haenszel test, stratified by PSADT (>6 months vs. ≤6 months), the use of a bone-sparing agent (Yes vs. No), and the presence of loco-regional disease (N0 vs. N1) at a two-sided 0.05 significance level.

The EQ-5D data will be summarized descriptively by treatment group and study visit.

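### The FACT-P test at 0.05 counts a 10-point drop at any time with no common window, so it partly measures how long each arm was observed

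*SAP*

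**What the plan says.** SAP 7.7.3 states that "any patient experiencing a 10-point decrease in FACT-P total scores from baseline at any post baseline time point will be considered" to have had a clinically meaningful deterioration. It then says that "the two treatment groups will be compared using a Mantel-Haenszel test, stratified by PSADT" and the other two randomization factors, at two-sided 0.05. Protocol 13.4.3 summarizes the proportion with at least a 10-point decrement, gives no time point, and adds: "The decrement in the FACT-P total score between treatment arms will be compared using a Mantel-Haenszel test, stratified by PSADT" and the same two other factors, at the same level.

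Four other places decide how long each patient is observed and which analysis governs:

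- **Collection.** FACT-P is completed at treatment visits, which continue until centrally reviewed metastasis or toxicity. After that, Protocol 8.9 says: "The FACT-P and EQ-5D questionnaires will be collected up to 12 months post-progression".
- **Cut at next therapy.** PRO SAP 2.5 by default keeps only scores from before subsequent therapy. Protocol 8.10 makes the next therapy readily available once metastasis is documented: "The Sponsor will provide abiraterone acetate to all other patients who meet the following criteria".
- **Companion analysis.** SAP 7.7.3 ends: "Details on the PRO analyses will be provided in a separate PRO SAP". PRO SAP 2.5.4 plans time to a 10-point FACT-P total deterioration, with censoring, Kaplan-Meier and stratified Cox. PRO SAP 1 says that it supplements the protocol and the SAP. It neither mentions nor withdraws the Mantel-Haenszel test.
- **Population.** The SAP says: "All FACT-P and EQ-5D data analyses will be performed in the ITT population". The protocol says: "All the analysis for FACT-P and EQ-5D data will be performed in the PRO population".

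**The concern.** A Mantel-Haenszel test on ever/never counts ignores time at risk. Observation ends with metastasis, or a limited time after it, and the trial is designed to make metastasis later on apalutamide (median MFS 25 vs 36 months). The arm observed longer fills in more questionnaires and has more chances to be counted as deteriorated. If the true deterioration hazards are equal, the expected proportions still differ, usually against apalutamide.

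Two errors follow: a false finding that apalutamide worsens quality of life, and a real benefit that goes undetected. Comparing patient-reported outcomes between arms is a stated objective, and this is the only FACT-P comparison given a significance level. FACT-P is an other evaluation outside the testing hierarchy, so the MFS and secondary conclusions are not at risk.

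**Working it through.** **Inputs from the documents.** 400 placebo and 800 apalutamide patients; placebo median MFS 25 months, HR 0.70; accrual over 24 months with 75% in the second year; minimum follow-up 9 months (SAP 4, Protocol synopsis and 13.6). SAP 7.7.3 gives no analysis date for FACT-P, so the primary MFS analysis is assumed: 24 + 9 = month 33.

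**Assumed.** No document gives a FACT-P deterioration rate. Exponential times with medians of 6, 12 and 24 months, equal in both arms, were used.

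**1. The plan's own figure.** Events = (1.960 + 1.282)² / [(1/3)(2/3)(ln 0.70)²] = 10.507 / 0.02827 = 371.7, i.e. 372 as stated. Median on apalutamide: 25/0.70 = 35.7 months, stated as 36.

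**2. Time observed.** The monthly MFS hazard is λ = ln 2/25 = 0.02773 on placebo and 0.7 × that = 0.01941 on apalutamide. Time C from entry to cut is uniform on 21–33 months (probability 0.25) or 9–21 months (0.75). If scores stop at metastasis, mean observation is E[1 − exp(−λC)]/λ:

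- placebo 0.3841/0.02773 = 13.85 months
- apalutamide 0.2898/0.01941 = 14.93 months

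Expected MFS events are 400 × 0.3841 + 800 × 0.2898 = 385, close to 372, so month 33 is a coherent date.

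**3. One case by hand.** Take a deterioration median of 12 months, so θ = ln 2/12 = 0.05776. The chance of being counted is E{θ/(θ+λ) × [1 − exp(−(θ+λ)C)]}: 51.1% on placebo, 54.2% on apalutamide. The pooled proportion is 0.5315 and SE = √[0.5315 × 0.4685 × (1/400 + 1/800)] = 0.0306. Expected z = 0.0303/0.0306 = 0.99, so the chance of a significant result against apalutamide is P(Z > 1.96 − 0.99) = 16.6%. With a true deterioration HR of 0.90 the proportions become 51.1% and 50.8%: the benefit vanishes.

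**4. Simulation on the scheduled visits.** 20,000 replicates per cell, Monte Carlo error at most 0.4 points, eight non-prognostic strata, every MFS event treated as metastasis. A drop is seen only at a questionnaire, so the rates are a little below the closed form. Ranges are for medians 24 to 6 months, with equal hazards.

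| Post-metastasis months kept | Mean observation, placebo vs apalutamide | Questionnaires | Gap in proportions (points) | False apalutamide worse (nominal 2.5%) |
|---|---|---|---|---|
| 0 | 13.85 vs 14.93 | 9.0 vs 9.4 | 1.9–3.1 | 9.4–20.4% |
| 4 | 15.25 vs 15.98 | 9.3 vs 9.6 | 1.2–1.5 | 5.6–8.2% |
| 12 | 17.09 vs 17.34 | 9.7 vs 9.9 | 0.3–0.4 | 2.9–3.4% |

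**5. Control.** With MFS HR set to 1.0, the false-worse rate is 2.5% for Mantel-Haenszel and 2.4% for log-rank. The excess therefore comes from unequal observation.

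**6. Time to deterioration on the same data.** The stratified log-rank gives 1.9–2.1% with equal hazards. Kaplan-Meier proportions at 12 months give 2.1–2.8%.

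**7. Power at an assumed true deterioration HR of 0.80.** Mantel-Haenszel vs log-rank:

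- 0 months kept: 25.0 vs 86.6%, 28.6 vs 72.1% and 23.0 vs 51.5% (medians 6, 12, 24)
- 4 months kept: 52.0 vs 88.3% and 47.3 vs 75.1% (medians 6, 12)

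**8. Other assumptions.**

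- *Visit-to-visit noise only* (5–25% per visit, within-patient correlation 0.5 or 0): Mantel-Haenszel 4.1–15.0% with 0 months kept and 3.3–6.2% with 12; log-rank 1.6–4.1%.
- *Metastasis and deterioration linked* (shared gamma frailty, variance 0.5 and 1, median 12), 0 months kept: Mantel-Haenszel 15.0 and 16.6%, log-rank 3.5 and 4.9%. With 12 months kept, log-rank 2.4 and 2.5%.
- *Deterioration hazard doubled after metastasis*, 12 months kept, median 12: 62.3% on placebo vs 61.4% on apalutamide, a real effect of delayed metastasis.

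**9. Separate precision point.** The change-from-baseline model in PRO SAP 2.5.5 omits the baseline score. With baseline correlation r and complete data, adding it lowers the per-visit variance by 1 − (1 + r)/2: 25% at r = 0.5 and 10% at r = 0.8 (assumed values).

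**The case against.** The strongest reply is that the large figures need a rule that this test may not have. Read literally, a drop at any post-baseline time point uses all 12 post-progression months, and the error is then close to nil at month 33. The high range requires the PRO SAP 2.5 cut to apply and next therapy to start soon after metastasis. No document gives that interval, and sponsor-supplied abiraterone depends on consent, country, investigator choice and no earlier subsequent treatment. This stands as a limit on size. It does not settle the matter, because the documents never say which rule the test follows.

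It is also fair that PRO SAP 2.5.4 already plans a sound comparison, so readers will see a censored hazard ratio beside the raw proportion. But the raw test keeps its 0.05 level, and nothing says which result governs if they disagree.

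Three smaller points stand. Protocol 13.4.3 does not say ever or any time, so that reading is inferred there. The log-rank test is not immune to informative censoring. The SAP change history shows that the move to ITT was deliberate, so on population only the protocol wording lags.

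**Conclusion.** The concern holds. Both documents attach a 0.05 test to a proportion without a common window, while observation length depends on the primary endpoint. At design values, month 33 and assumed deterioration medians of 24 to 6 months, the false apalutamide-worse rate is 9.4–20.4% if scores stop at metastasis, 5.6–8.2% with 4 further months and 2.9–3.4% with 12, against 2.5%. With 0 months kept, power for a true HR of 0.80 is 23–29% instead of 52–87%.

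The mechanism is certain. The size rests on the assumed rates and on how much post-metastasis data is used. The plan should be changed, but no confirmatory conclusion depends on it.

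**What to change.** 1. In SAP 7.7.3 and Protocol 13.4.3, make the time to 10-point FACT-P total deterioration from PRO SAP 2.5.4 the between-arm comparison: stratified log-rank and Cox, with Kaplan-Meier proportions at fixed times such as 6 and 12 months. Label the any-time proportion descriptive, and show observation time and number of questionnaires by arm. Align the analysis population in the same edit.
2. State in SAP 7.7.3 that the PRO SAP 2.5 cut at subsequent therapy applies. Add a sensitivity analysis using all questionnaires up to 12 months post progression, because censoring at new therapy may be informative.
3. Separately, for precision, add the baseline score as a covariate in the PRO SAP 2.5.5 model.

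The cost is wording in three places. The protocol must change with the SAP, or the two will conflict. No new data are needed: the time-to-deterioration analysis is already planned, post-progression questionnaires are already scheduled, and baseline scores are collected on Cycle 1 Day 1.

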7.7.4 Population Pharmacokinetic Analyses

A separate Population PK analysis plan will be prepared prior to database lock. A separate report will be generated.

7.7.5 Exploratory Biomarker Analyses

Biomarker analyses are exploratory and data generated will be reported separately.

7.7.6 Assessment of Ventricular Repolarization

The assessment of ventricular repolarization will be a sub-study conducted in a subset of patients from selected clinical sites and analyzed by an independent cardiac safety laboratory. Description of the sub-study is provided in Appendix 8 of the study protocol. A separate analysis plan will be prepared.

7.7.7 Medical Resource Utilization Analysis

Protocol-mandated procedures, tests, and encounters are excluded. The MRU data may be used to conduct economic analyses.

ARN-509-003 Statistical Analysis Plan v7.0 26 June 2017

Page 20 of 34

7.8 SENSITIVITY ANALYSES

Sensitivity analyses will be performed on the primary efficacy endpoint of MFS and secondary endpoint of OS to support the results in the primary analysis.

7.8.1 Investigator-Derived MFS

A sensitivity analysis will be performed on the primary endpoint of MFS using the investigator-derived progression (development of metastasis or death). Patients without a MFS event will be censored on the known date of progression-free according to the investigator tumor assessment.

7.8.2 OS

Sensitivity analyses for the OS may be carried out as appropriate if it is deemed useful to aid in the interpretation of the results.

7.8.2.1 Covariate Effects

A non-stratified multivariate analysis will be performed on the OS endpoint to estimate treatment effect adjusting for important baseline factors. The following baseline covariates will be considered:

- PSADT (≤ 6 months vs. > 6 months)
- Bone-sparing agent use (Yes vs. No)
- Loco-regional disease (N0 vs. N1)
- ECOG Performance status (0 vs. 1)
- Number of prior hormonal therapies $(1 \text{ vs.} \ge 2)$
- Gleason score ($\leq 7 \text{ vs.} \geq 8$)
- Age (continuous)
- Logarithm of PSA (continuous)

The adjusted hazard ratio and its 95% confidence interval for treatment and each factor will be estimated using Cox regression.

7.8.2.2 Other Sensitivity Analyses for OS

A large number of subjects are expected to receive life-extending subsequent therapies, the following analyses may be used in estimating the true treatment effect.

- 1. Inverse Probability of Censoring Weighted (IPCW) log-rank Tests by Robins et al^{12,13,14,15} will be used to estimate the treatment effect and its associated confidence interval.
- 2. Using a time-dependent Cox regression; the HR prior to receiving subsequent anticancer therapy and after receiving the subsequent anticancer therapy will be estimated, the associated 95% confidence interval will also be calculated.

Additional analyses may be performed for OS if appropriate.

ARN-509-003 Statistical Analysis Plan v7.0 26 June 2017

Page 21 of 34

7.8.3 Subgroup Analyses

In order to assess the consistency of treatment benefit with respect to the primary efficacy endpoint of MFS and secondary endpoint of OS across important subgroups, forest plots will be provided for the following variables:

- ECOG performance status (0 vs. 1) at baseline
- Age category (< 65 vs. \geq 65 years and < 75 vs. \geq 75 years)
- Race (white, black, Asian, and others)
- Geographic region (NA, EU, and ROW)
- Number of prior hormonal therapies $(1 \text{ vs.} \ge 2)$
- Baseline PSA value (at or below median vs. above median)
- PSADT (> 6 months vs. \leq 6 months)
- Bone-sparing agent use (Yes vs. No)
- Loco-regional disease (N0 vs. N1)

The comparison between treatment groups will be evaluated by a single hazard ratio with its 95% confidence interval based on a non-stratified Cox regression model for each subgroup.

7.9 ANALYSIS BY FORMULATION

During the conduct of the study, treatment formulation was switched from capsule to tablet, at which time a significant number of subjects have been already enrolled and have received capsule formulation. The randomization and blinding remained unchanged during the formulation switch. Newly enrolled subjects began treatment using tablets while subjects already enrolled and receiving capsules made the switch to tablets at the start of a new cycle.

As outlined in previous sections, the primary analyses will be based on the Safety and ITT Populations irrespective of the formulation switch. However, to show that the two formulations have no clinically relevant impact on key efficacy and safety data, supplemental descriptive analyses will be performed. For safety analyses, the descriptive analysis by formulation subgroups (capsule only, capsule/tablet, and tablet only) will be performed.

7.9.1 Subject Distribution by Formulation

For each formulation subgroup the following summaries by treatment group will be generated:

- Number of subjects randomized, treated, discontinued and ongoing
- Primary reasons for study treatment discontinuation

7.9.2 Demographics and Baseline characteristics by Formulation

The parameters outlined in section 7.4.1 will be summarized by treatment group and formulation. The summary will include subjects as randomized.

ARN-509-003 Statistical Analysis Plan v7.0 26 June 2017

Page 22 of 34

7.9.3 Study Drug Administration by Formulation

Descriptive statistics will be provided on dose modifications by treatment group and formulation and the subjects will be included as treated.

7.9.4 Safety Analyses by Formulation

The by-formulation safety analysis will use subjects as treated and will include the following AEs summaries:

- Overall summary of AEs (See Appendix 2 for table shell)
- All AEs by System Organ Class (SOC), Preferred Term (PT) and toxicity grade
- Grade 3/4 AEs by SOC, PT and toxicity grade

7.9.5 Efficacy (MFS and PSA Response) Analyses by Formulation

The primary MFS analysis and statistical inference will be based on the ITT population regardless of the formulation as defined in section 7.5.2. In order to assess the consistency of treatment benefit (relative to ITT analysis), a supplemental analysis by formulation subgroup will be performed on the BICR derived MFS endpoint and PSA response.

The following formulation subgroups will be used in the analysis:

- 1. Capsule only, tablet only and capsule + tablet
- 2. Two groups based on greater duration of exposure on specific formulation: greater duration on capsule versus greater duration on tablet.

The MFS subgroup analysis will include the following:

- Number of events and censored
- Distribution of MFS endpoint using the Kaplan-Meier method
- Non-stratified estimate of the hazard ratio and its associated 95% confidence interval using the Cox model.

ARN-509-003		
Statistical Analy	sis Plan v7.	0 26 June 2017

Page 23 of 34

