Rationale: Collection of MRU should continue during the Long-term Follow-up Phase.	
Section 8.9 Long-term Follow-up; Appendix 1, Schedule of Activities	Added collection of MRU to the Long-term Follow-up Phase.
Rationale: The Survival Follow-up includes collection of other information and referring to this phase as Survival Follow-up was not accurate.	
Synopsis Study Design, Duration of Patient Participation and Duration of Study; Section 4.1 Inclusion Criteria; Section 8.9 Long-term Follow-up; Section 10 End of Treatment; Section 15.6 End of Trial in all Participating Countries; Appendix 1, Schedule of Activities	Revised the name of this phase of the study to “Long-term Follow-up Phase.” Inclusion Criterion #13.2 was revised to the following: Willingness and ability to comply with scheduled visits, treatment plans, laboratory and radiographic assessments, and other study procedures, including ability to swallow study drug tablets, the completion of patient reported outcomes questionnaires and <del>survival long-term follow-up visits</del>

Applicable Section(s)	Description of Change(s)
Rationale: If thyroid stimulating hormone (TSH) levels are abnormal, additional reflex testing must be performed.	
Section 8.5 Every 16 weeks...; Appendix 1 Schedule of Activities; Footnote 11; Appendix 2	Added the following statement to Appendix 2: If TSH is abnormal; total T3, free T4 (direct), and total T4 are required. Added reference to Appendix 2 in Footnote 11 of Appendix 1
Rationale: SAE reporting requirements were not aligned with the current Janssen protocol template.	
Section 9.2.1 SAE Reporting	Made the following revision: Information regarding SAEs will be transmitted to the Sponsor using the Serious Adverse Event Form, which must be completed and signed by a physician from the study site, and transmitted to the Sponsor within 24 hours. The initial and follow-up reports of an SAE should be made by facsimile (fax). This timeframe also applies to additional new information (follow-up). SAEs should be reported by facsimile or email.
Rationale: All patients will have switched from softgel capsules to tablets at the time of implementation of this amendment therefore guidance for the switching, is no longer necessary.	
Section 5.3.3 Drug Administration	Removed guidance for the switch from softgel capsules to tablets.
Rationale: A generic name for ARN-509 is now available.	

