The overall reason for this amendment is to switch softgel capsules to tablets (commercial formulation) for patients currently receiving the softgel capsules and to administer tablets to newly enrolled patients. Added the restriction that Section 8.10 does not apply in Japan. Additional minor changes were made as outlined below.

Applicable Section(s)	Description of Change(s)
Rationale: Switch of softgel capsules to tablets is incorporated. (b) (4) is not included in the tablet formulation.	

Applicable Section(s)	Description of Change(s)
Throughout	Changed “softgel capsules” or “capsules” to “tablets.”
Section 5.3.1 ARN-509/Matched Placebo; Section 5.3.2 Packaging, Storage, and Labeling	Removed information on formulation, packaging, and storage of the softgel capsules. Replaced with appropriate wording for the tablets.
Section 5.3.1 ARN-509/Matched Placebo; Section 6.2, Restricted Therapies; Appendix 5	Removed (b) (4) information, no longer applicable with the tablet formulation.
Section 5.3.3 Study Drug Administration	Added a new table showing the conversion from capsule to tablet and clarifying that the conversion is 2:1. Provided timing for the switch from the softgel capsules to tablets. Revised Table 2.
Rationale: The twice daily dosing is no longer relevant for the tablet formulation.	
Synopsis Dose and Route of Administration; Section 5.3.4 Cycle Management; Section 5.3.5 Dose Modifications	Removed the twice daily dosing option. Removed wording on dose modification due to gastrointestinal discomfort.
Rationale: Revised treatment compliance to account for capsules or tablets	
Section 5.5 Measures of treatment compliance; Schedule of Activities (Footnote 8)	Changed from “capsules” to “capsules or tablets.” Revised compliance to account for the difference in number of capsules versus tablets.
Rationale: The Statistical Analysis Plan will include additional analyses for safety and for the primary endpoint by formulation subgroup.	
Section 13.2.1 Analysis of Primary Endpoint	Added the following sentence: Additional analyses by formulation subgroups will be performed for the MFS endpoint as described in the Statistical Analysis Plan.
Section 13.3.1 Analysis of Adverse Events	Added the following sentence: An additional analysis by formulation subgroups will be performed as outlined in the Statistical Analysis Plan.

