2. STUDY DESIGN

This is a randomized (2:1), multicenter, double-blind, placebo-controlled, Phase III clinical trial evaluating the efficacy and safety of ARN-509 versus placebo in approximately 1200 men with high risk non-metastatic (M0) castration-resistant prostate cancer (NM-CRPC), defined as PSA Doubling Time (PSADT) \leq 10 months.

ARN-509 will be administered orally on a continuous daily dosing schedule, at a starting dose of 240 mg per day in the treatment group. Matched placebo will be administered orally on a continuous daily dosing schedule, at a starting dose of 240 mg per day in the placebo group.

Patients will be followed for safety and efficacy as per the schedule of assessments and will remain on study treatment until documented radiographic progression (development of distant metastases as assessed by blinded independent central review [BICR]) or the development of unacceptable toxicity.

Patients discontinuing treatment due to documented radiographic progression will enter the survival follow-up period, where they will be followed for the development of symptomatic progression, initiation of subsequent anti-cancer therapies (in particular, cytotoxic chemotherapy) every 4 months until death, loss of follow-up, or withdrawal of consent, whichever comes first.

Patients discontinuing treatment prior to documented radiographic progression will also enter the survival follow-up period where they will continue to have scheduled disease assessments every 4 months until documented radiographic progression, and will be followed for the development of symptomatic progression and initiation of subsequent anti-cancer therapies (in particular, cytotoxic chemotherapy) every 4 months until death, loss of follow-up, or withdrawal of consent, whichever comes first.

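### SAP 7.9.5 compares MFS in formulation groups that, apart from tablet only, depend on time on treatment, so the capsule-only curves and hazard ratio say nothing about formulation

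*SAP*

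**What the plan says.** SAP 7.9.5 asks for a supplemental analysis of BICR-based MFS by formulation, to check consistency of benefit with ITT. It gives two groupings: "Capsule only, tablet only and capsule + tablet", and "Two groups based on greater duration of exposure on specific formulation: greater duration on capsule versus greater duration on tablet". Each group gets event counts, Kaplan-Meier curves and an unstratified Cox hazard ratio with its 95% CI. SAP 7.9 states the wider aim: "to show that the two formulations have no clinically relevant impact on key efficacy and safety data".

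On how men came to be in each group, SAP 7.9 puts later enrollees on tablets from the outset. Of the men who had begun on capsules it says: "subjects already enrolled and receiving capsules made the switch to tablets at the start of a new cycle". In the protocol's amendment history, Amendment INT-6 (18 May 2015) introduced the change. The rationale of Amendment 7 (1 June 2016) then takes it as complete: "All patients will have switched from softgel capsules to tablets at the time of implementation of this amendment". I use the amendment history only to date the switch.

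SAP 2 says that patients "will remain on study treatment until documented radiographic progression". SAP 7.5.2 times MFS from randomization to BICR-confirmed distant metastasis or death. SAP 7.9 and its subsections contain no landmark, delayed entry, time-dependent formulation term, grouping by starting formulation or caveat. They do say that the primary analyses ignore formulation and that these analyses are descriptive.

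**The concern.** A capsule starter stays in capsule only if his treatment ended before the switch, and one common way for it to end is the MFS event. He becomes capsule plus tablet only if he was still on treatment at the switch, which builds in event-free time on treatment. Greater duration on capsule also takes in men whose treatment ended soon after the switch. Membership therefore depends on the outcome, on other reasons for stopping and, through both, on the arm. This is immortal-time and selection bias. Only tablet only is fixed at entry.

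At stake is the reading of the display. Very short capsule-only medians would look like poor capsule performance. A capsule-only hazard ratio near ITT would look like reassurance. Neither reading would be justified. The point concerns MFS; I make no claim about PSA response.

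**Working it through.** **1. Plan's own figure.** Events for 90% power at HR 0.70, two-sided alpha 0.05, 2:1: (1.960 + 1.282)² / [(2/3)(1/3)(ln 0.70)²] = 10.51 / (0.2222 × 0.1272) ≈ 372, as in SAP 4. Under exponential times the apalutamide median is 25/0.70 = 35.7 months.

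**2. Simulation inputs from the documents.** Placebo median 25 months, HR 0.70, 2:1, 24-month accrual with 75% in year 2 (SAP 4), and 9 months' minimum follow-up (Protocol synopsis), so a cut at month 33. Treatment ends at the MFS event, at other stopping or at the cut. Men who stop early stay under scan follow-up (Protocol 3.1). The formulations are identical by construction.

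**3. Assumptions not in the documents.**
- Switch at accrual month 15, 18 or 21. A switch at month 24 would leave no tablet starters, contrary to SAP 7.9.
- Other stopping. Protocol 1.1.3 reports 8 of 51 men stopping for adverse events; taking the 15-month median follow-up given there as applying to that count, −ln(1 − 8/51)/15 = 0.0114 per month. Placebo stopping is unknown, so several patterns are shown.
- Hazard after early stopping: either the drug effect persists, or the hazard returns to the placebo level.

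**4. Capsule-only hazard ratio** (ranges span switch months and repeat runs):

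| Other stopping per month | Effect persists (ITT about 0.70) | Hazard returns to placebo (ITT 0.69–0.75) |
|---|---|---|
| Equal, 1.14% | about 0.79 | 0.84–0.86 |
| Equal, 2.2% | 0.75–0.77 | 0.83–0.85 |
| Placebo 0.57%, apalutamide 1.14% | 0.62–0.64 | 0.66–0.69 |
| Placebo 1.14%, apalutamide 0.57% | 1.05–1.08 | about 1.10–1.12 |
| None | 0.96–0.99 | 0.97 |

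Where there is other stopping, 50–75% of capsule-only men ended treatment through the MFS event itself; with none, all did.

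**5. Medians.** Capsule-only placebo medians are about 3.5–8.5 months against 25. With the effect persisting, capsule-only apalutamide medians are about 3.7–12.4 against 35.7. Capsule plus tablet shifts the other way: placebo median 30–33 months or not reached.

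**6. Other hazard ratios, effect persisting.** Greater duration on capsule, in the row order above: 0.73–0.78, 0.72–0.75, 0.64–0.69, 0.79–1.02, 0.75–0.95. Capsule plus tablet 0.68–0.71; greater duration on tablet 0.67–0.71; tablet only 0.68–0.71. All capsule starters pooled: 0.69–0.71. If the hazard returns to placebo, the pooled figure is 0.70–0.76 and tracks ITT within about 0.01.

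**7. At trial size** (N = 1,200, equal 1.14%, effect persisting), capsule only has 88–209 patients and 70–161 events. Its hazard ratio exceeds 0.85 in 33–38% of trials, against 12–22% for an unbiased group with as many events. Its 95% CI excludes 0.70 in 7–12%, against 5%. Its placebo median lies within about 3–9 months in 95% of trials.

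**8. Variants, effect persisting.**
- Document dates: 18 May 2015 to the SAP date of 26 June 2017 is 25 months; to 1 June 2016 is 12.5 months. With the cut 25 months after the switch, and switching immediate or spread over 12.5 months, the capsule-only hazard ratio is 0.79–0.80 at equal 1.14% and 0.64–1.05 over all patterns. The placebo median is 3.6–11.0 months.
- Events seen only at 16-week scans: 0.81 at equal 1.14%, 0.65–1.05 over all patterns.
- US censoring, bounded by censoring every early stopper at stopping: 0.86–0.87 at equal 1.14%, 0.75–1.05 with two-fold unequal rates.

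**The case against.** The strongest reply is that little hangs on this. The analysis is supplemental and descriptive, with no test or margin. It is read as an arm contrast within groups, not as a comparison of medians between groups. A clear conflict with ITT would be uncommon, as step 7 shows, and Protocol 13.4.4 also explores formulation in the population PK model. All of that stands and limits the reach. It does not rescue the capsule-only result, because SAP 7.9.5 plans the curves as well as the hazard ratio, and neither can serve the stated aims.

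A second reply is that the inputs are largely assumed. That also stands. The direction of the hazard-ratio bias cannot be predicted, the ranges are not bounds, and ITT rather than a fixed 0.70 is the comparator. One might expect more equal stopping to bring the capsule-only ratio back to ITT, but if the hazard returns to placebo it barely moves (0.84–0.86 to 0.83–0.85). Dependence on unknown stopping behaviour is itself the reason not to interpret this ratio. The collapse of the curves appears in every case.

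A third reply is that grouping by starting formulation has faults of its own, and that the greater-duration split followed FDA feedback recorded in the SAP's summary of changes. Both are true. The fix keeps that split and states the faults.

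A reader might go further and infer that every formulation subgroup is invalid or that the primary result is compromised. The documents do not support this. Tablet only is fixed by enrolment date, the capsule-plus-tablet hazard ratio stays near ITT, and SAP 7.9.5 rests inference on ITT regardless of formulation.

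**Conclusion.** The concern holds for the capsule-only curves and hazard ratio, for the greater-duration-on-capsule hazard ratio in part, and for the Kaplan-Meier curves of every group whose membership depends wholly or partly on time on treatment. The mechanism follows from the SAP alone. The sizes rest on exponential times, the design assumptions, and the assumed switch month, placebo stopping and post-stopping hazard. Under them, capsule-only placebo medians of a few months are near certain with no formulation effect, and the hazard ratio can miss ITT in either direction or match it by coincidence.

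A reader might also infer that the capsule-only ratio is always pulled towards 1. It is not: with twice the stopping on apalutamide it falls below ITT. This is a worthwhile, inexpensive improvement to a supplemental analysis. It changes no conclusion about the primary endpoint.

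**What to change.** Add to SAP 7.9.5 the treatment effect on MFS by formulation at first dose (capsule start versus tablet start), and name it as the grouping used to judge consistency with ITT. It is fixed at baseline, pools capsule only with capsule plus tablet, and leaves tablet only unchanged. Keep all planned displays, including the greater-duration split, with this footnote on every group except tablet only:

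> Membership depends wholly or partly on time on treatment after randomization; Kaplan-Meier curves, and the hazard ratios for capsule only and greater duration on capsule, are subject to immortal-time and selection bias and are not evidence for or against a formulation effect.

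The work is SAP wording, one pooled grouping to program and one footnote. The downsides are:
- **Dilution.** Capsule starters spend 69%, 63% and 55% of treatment time on tablets for a switch at month 15, 18 and 21 (46–74% on the document dates), so a true difference would be muted.
- **Period.** Capsule starters include men enrolled before the mid-2014 eligibility changes (Amendments INT-4 and INT-5); tablet starters do not.
- **Size.** The tablet-start group has about 675 patients and 173 events, 450 and 105, or 225 and 47, for those switch months.
- **Weight.** The split adopted after FDA feedback carries less interpretive weight.
- **Limit.** Agreement by starting formulation shows consistency with ITT, not equivalence.

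Censoring all capsule starters at the switch date would reduce dilution, but it needs a site switch date for men already off treatment. The documents do not show that one is recorded, so I would not add that analysis unless it is.
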